2.3.2 Secondary

1. To determine the safety and tolerability of MVC and DTG when added to a stable ART regimen. The safety and tolerability measures will include time to discontinuation of any study medication due to adverse events (AEs), proportion of Grade 3 or Grade 4 clinical AEs, proportion of Grade 3 or Grade 4 laboratory abnormalities, and summaries of all treatment related AEs.
2. To determine whether intensification with MVC and DTG will improve neurocognitive functioning at weeks 24, 72, and 96.
3. To determine whether functional status improves at week 48 after intensification with MVC and DTG (Arm C) to a greater extent than when intensified with DTG and placebo for MVC (Arm B) or placebo of both drugs (Arm A).
4. To assess the effect of adding MVC and DTG on biomarkers in peripheral blood and CSF.
5. To assess the association between **plasma** and CSF biomarkers, neuropsychological performance, and DTG and MVC pharmacokinetics (PK) throughout the course of the study.
6. To assess whether the addition of DTG alone (Arm B) or DTG and MVC (Arm C) is associated with maintenance of plasma HIV-1 RNA <50 copies/mL.
7. To assess changes in blood CD4+/CD8+ counts after intensification with DTG and MVC (Arm C), DTG alone (Arm B) or placebos (Arm A).
8. To determine associations between peripheral blood immunologic markers (s100 β , soluble CD14) and changes in neurocognitive function at week 48.
9. To determine the relationship between changes in CCR5 ligand levels (MIP-1b) and inflammatory marker changes in both peripheral blood and CSF.
10. To determine the effect of DTG intensification on residual viremia, cellular HIV-1 RNA expression, total cellular HIV-1 DNA, and 2 long terminal repeat sequences (LTR) DNA, and to determine whether these virologic changes are associated with week 48 neurocognitive function.

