2.4 Overview of Sample Size Considerations

Based on previous studies, a standard deviation (SD) of 0.7 in the 48-week change in normalized neurocognitive test score is assumed. In the sample size calculation, the null hypothesis is that there is no difference in changes of neurocognitive functioning from baseline to week 48 across the treatment arms, while the alternative hypothesis is that the change of neurocognitive functioning is at least 0.5 higher for the (MVC and DTG) arm. A Bonferroni correction has been applied to account for multiple comparisons between treatments. One interim analysis of efficacy

is planned in the middle of the study and the adjusted sample sizes assume a 15% loss to follow-up. To achieve a power of 90%, we would expect a sample size of 62 participants per group for a total 186 participants on study. See Protocol section 9.4 for further details.

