3.1 Primary Outcome Measures

1. The change in normalized composite neurocognitive test score at week 48 from pre-entry. This test score is further defined below.
 - Aligns with Primary Objectives 1 & 2

The normalized neurocognitive test score for domestic participants is defined as the average of z-scores on the following tests:

- Stroop color naming [English: NE7041, Spanish: NE7101]
- Stroop word reading [English: NE7041, Spanish: NE7101]
- Stroop interference trial [English: NE7041, Spanish: NE7101]
- Grooved pegboard dominant [NE7046]
- Grooved pegboard non-dominant [NE7046]
- HVLTR Learning trials [NE7097]
- HVLTR Delayed recall [NE7097]
- HVLTR Delayed recognition [NE7097]
- Semantic verbal fluency [NE7098]
- Letter fluency [NE7098]
- Trail Making A [NE7099]
- Trail Making B [NE7099]
- WAIS-III Symbol search [NE7101]
- Digit Symbol [NLW0016]

The WRAT-4 word reading total [English: NLW0018] (WAT Spanish Word List word reading total [Spanish: NLW0020]) was also administered at domestic sites but will not be included in the average z-score calculation and instead will be analyzed separately.

The normalized neurocognitive test score for international participants is defined as the average of z-scores on the following tests:

- Grooved pegboard dominant [NE7046]
- Grooved pegboard non-dominant [NE7046]
- HVLTR Learning trials [NE7097]

- HVLT-R Delayed recall [NE7097]
- HVLT-R Delayed recognition [NE7097]
- Semantic verbal fluency [NE7098]
- Digit Symbol [NLW0016]
- Timed Gait [NE7090]
- Finger Tapping Dominant [NE7095]
- Finger Tapping Non-dominant [NE7095]
- Color Trail 1 [NE7096]
- Color Trail 2 [NE7096]

The International HIV Dementia Scale (IHDS) [NE7061] was also administered at international sites but will not be included in the average z-score calculation and instead will be analyzed separately.

For time point assessment of impairment (baseline, weeks 24, 48, 72, 96), z-scores will be calculated by subtracting a demographically appropriate (adjusted for age, race, sex, and years of education) norm and dividing by a demographically appropriate standard deviation. Z-score calculations are described in detail in Section 0. The z-scores will be calculated using the raw scores from the neurocognitive tests.

Assessment of change over time in neurocognitive impairment will be calculated by subtracting the average z-scores of the two time points of interest.

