3.3 Other Outcome Measures

1. Changes from baseline to week 48: residual viremia, cell-associated HIV-1 RNA/DNA/2-LTR circles and SCA, T-cell and monocyte activation.
 - Aligns with Secondary Objective 10
 - Looking specifically at the comparison between DTG only arm and placebo arm to determine the effect of DTG intensification on these factors
 - **NOTE: This outcome measure was listed as secondary in the protocol but the intention was as an exploratory outcome due to lack of funding for testing, specifically for T-cell and monocyte activation**
2. Beck Depression Inventory (BDI) evaluations
 - **New outcome measure**
 - **Change in BDI score (evaluated as the sum of the 21 items) from baseline to weeks 24, 48, 72, and 96**
 - **Change from baseline in BDI score by subscales:**
 - Cognitive (items 1, 2, 3, 5, 6, 7, 8, 9, and 14)
 - Affective (items 4, 10, 12, and 13)
 - Somatic (items 11, 15, 16, 17, 18, 19, 20, and 21)
 - **Percent of participants with a BDI score \leq 13 vs. $>$ 13 at weeks 24, 48, 72, and 96**
3. **Associations of neuropsychological performance with plasma and CSF biomarkers and at weeks 0, 24, 48, 72, and 96 (0 and 48 only for CSF biomarkers); and with DTG and MVC PK at weeks 24 and 48.**
 - **Aligns with Secondary Objectives 5, 8, 9**

4 Statistical Principles

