4.2.3 Other Analyses

1. Changes in virologic measures: Wilcoxon rank-sum test will be used to compare Arm A and Arm B to assess the effect of DTG intensification on virologic changes.
2. **BDI Analyses: Change will be compared pairwise among the three treatment arms using the Wilcoxon rank-sum test. Percent of participants with BDI score >13 vs ≤ 13 will be compared by arm using the Chi-Square test.**

3. Correlation Analyses: Spearman correlations and scatterplots will be used to assess associations between:
 - a. Peripheral blood and CSF biomarkers and neuropsychological performance at weeks 0, 24, 48, 72, 96 (weeks 0 and 48 only for CSF biomarkers).
 - b. Changes in blood immunologic markers and changes in neurocognitive performance from baseline to week 48.
 - c. Changes in blood biomarkers from baseline to week 48.
 - d. **DTG and MVC PK and neuropsychological performance at weeks 24 and 48.**

5 Report Contents

Detailed descriptions of the content for each of the following sections are given in the AIP.

- CONSORT Diagram
- Accrual – summarize enrollment
- Baseline characteristics
 - Age
 - Sex
 - Race
 - IV drug use
 - Country
 - Education
 - Primary Language
 - HAND diagnosis
 - Nadir CD4 count
 - CD4 count
 - Log10 HIV-1 RNA
 - Neurocognitive test score
- Study status
- Treatment status
 - Premature study treatment discontinuation reasons
- Study conduct
 - Missed visits
- Safety Summary
- Analysis of primary outcome measures
 - Subgroup analyses
 - Sensitivity analyses
- Analysis of secondary outcome measures
- Analysis of other outcome measures

6 Appendix: Neuropsychological Norms For ACTG A5324

Domestic Sites

Trail Making A & B, Grooved Pegboard, Semantic and Letter Fluency

Norm source: Heaton RK, Miller SW, Taylor MJ, Grant I. (2004). Revised comprehensive norms for an expanded Halstead-Reitan battery: demographically adjusted neuropsychological norms for African American and Caucasian adults. Lutz, FL: American Psychological Assessment Resource, Inc.

- T scores were generated using the manual look-up tables.
- T scores were then converted to z-scores.
- Norms for African Americans were used for Hispanic and Native American participants.
- Trails B used a cut-off time of 240 seconds instead of the expected time out score of 300 seconds. Scores ≥ 240 are imputed to 300 for calculating the T score (unless a comment from the site provides an exact time).

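### The exploratory PK correlation uses the level of neuropsychological performance at weeks 24 and 48 without adjusting for pre-entry performance, which dilutes a true exposure effect and leaves it open to adherence confounding

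*SAP*

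**What the plan says.** SAP section 4.2.3, item 3, gives one method for all its correlation analyses: "Spearman correlations and scatterplots will be used to assess associations between" the listed pairs. Item 3d is "DTG and MVC PK and neuropsychological performance at weeks 24 and 48". The matching outcome in section 3.3, item 3, reads "and with DTG and MVC PK at weeks 24 and 48". It is aligned with Secondary Objective 5 (section 2.3.2), which covers "neuropsychological performance, and DTG and MVC pharmacokinetics (PK) throughout the course of the study".

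Neither place mentions change from pre-entry, a baseline covariate, a partial correlation or adherence. Neither says which arms enter the PK correlation.

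Two neighbouring items show that level is the natural reading. Item 3b uses change explicitly: "Changes in blood immunologic markers and changes in neurocognitive performance from baseline to week 48". Item 3a uses the same performance-at-week form as 3d and includes week 0, which can only be a level.

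The composite is otherwise handled as a change: the primary outcome is "The change in normalized composite neurocognitive test score at week 48 from pre-entry", and section 3.2, item 2, uses change from baseline for the composite and domain scores.

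**The concern.** Participants add study drug to their ART at entry (SAP section 2.1), so a concentration at week 24 or 48 can only have affected what happened after entry. The score at that visit also carries the participant's pre-entry cognition, which ranges from asymptomatic impairment to dementia. It also carries any offset between the domestic and international batteries and norm sources (SAP sections 3.1 and 6).

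Two consequences follow. First, pre-entry variation unrelated to drug dilutes a true exposure effect. Second, if better cognition goes with better pill-taking, PK and performance correlate with no drug effect at all. The documents make that route plausible: the IADL scale in SAP section 7, item 14, treats keeping track of medication as something that can be impaired. Adherence is assessed (Protocol, letter-of-amendment text for section 6.2.3) but is not used in item 3d.

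What is at stake is interpretation. A null correlation could be dilution, and a positive one could be adherence.

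**Working it through.** **Inputs from the documents.** There are 62 participants per arm, 15% loss, and "a standard deviation (SD) of 0.7 in the 48-week change in normalized neurocognitive test score is assumed" (SAP section 2.4). DTG is given in Arms B and C, MVC in Arm C only (section 2.1).

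**Plan's own figure.** No sample size, power or detectable correlation is given for the PK analysis. The 62 per arm, used below, does reproduce if the Bonferroni level is read as two-sided 0.05/3: 2 × (0.7 × (2.394 + 1.282) / 0.5)² = 52.96, and 52.96 / 0.85 = 62.3.

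**Numbers with PK.** DTG: 124 × 0.85 ≈ 105. MVC: 62 × 0.85 ≈ 53. This assumes PK on every retained participant, which the supplied text does not state.

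**Assumptions not in the documents.** Pre-entry to follow-up correlation ρ of 0.6 to 0.8; exposure-change correlation 0.30; equal variances at both visits; PK-cognition correlation c of 0.2 to 0.3 for the confounding case.

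**Dilution.** The level SD implied by a change SD of 0.7 is 0.7 / √(2(1−ρ)): 0.78 at ρ = 0.6 and 1.11 at ρ = 0.8. If exposure is independent of pre-entry score:

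- r(level) = r(change) × √(2(1−ρ))
- r(adjusted) = r(change) × √(2/(1+ρ))

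Power is by Fisher z with variance 1.06/(n−3), two-sided 5%, n = 105:

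| ρ | r level / change / adjusted | Power level / change / adjusted |
|---|---|---|
| 0.3 | 0.355 / 0.300 / 0.372 | 0.95 / 0.86 / 0.97 |
| 0.6 | 0.268 / 0.300 / 0.335 | 0.77 / 0.86 / 0.93 |
| 0.8 | 0.190 / 0.300 / 0.316 | 0.47 / 0.86 / 0.89 |

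For MVC (n = 53) at ρ = 0.6 to 0.8, power is 0.47 to 0.26 for level, 0.57 for change and 0.67 to 0.61 adjusted.

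Change beats level only when √(2(1−ρ)) < 1, that is, ρ > 0.5. Adjusted over level is 1/√(1−ρ²), which exceeds 1 at any positive ρ.

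**Confounding with no drug effect, n = 105.** The result depends on what PK follows.

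*PK follows the measured pre-entry score.* r(level) = cρ, from 0.2 × 0.6 = 0.12 to 0.3 × 0.8 = 0.24. r(change) = −c√((1−ρ)/2), from −0.063 to −0.134. The adjusted correlation is 0.

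*PK follows stable cognition*, so it correlates c with the score at both visits. r(level) = c, 0.2 to 0.3. r(change) = 0. r(adjusted) = c(1−ρ) / √((1−c²)(1−ρ²)), from 0.068 (c = 0.2, ρ = 0.8) to 0.157 (c = 0.3, ρ = 0.6).

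Probability of rejection at a nominal 5%:

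| PK follows | Level | Change | Adjusted |
|---|---|---|---|
| Measured pre-entry score | 22-67% | 10-26% | 5% |
| Stable cognition | 51-86% | 5% | 10-34% |

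**Cross-check.** A simulation (1,500 runs per setting, rank-based tests) agreed. With PK following the measured score it gave 23-68% for level, 11-26% for change and 4-6% adjusted. With c defined against the underlying trait, a weaker link to the measured scores (c√ρ), it gave 34-77%, about 5% and 10-23%.

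**The case against.** The strongest case against is about weight. The analysis sits under Other Outcome Measures and is described as correlations and scatterplots, with no alpha and no decision attached. The per-protocol analysis in SAP section 4.2.1 already looks at incomplete treatment for the primary outcome. The Analysis Implementation Plan, which is not among the documents, might define the variable. All of this stands and makes the point minor. It does not change what item 3d says.

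A reader might infer more than the documents support:

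- *That adjustment removes adherence confounding.* It does so only if PK follows the measured pre-entry score. Otherwise 10-34% false rejection remains.
- *That level is always worse than change.* This fails for ρ below 0.5, and the documents do not give ρ.
- *That the level is mostly pre-entry cognition.* At ρ = 0.6, pre-entry score explains 0.6² = 36% of follow-up variance.
- *That the plan uses change for every outcome.* Plasma HIV-1 RNA at or above 50 copies/mL (section 3.2, item 5) and BDI above 13 (section 3.3, item 2) are compared as levels.
- *That this is the only exposure-response analysis, or that it decides how a null primary result is read.* SAP section 1.1 sends other objectives to a separate SAP, and nothing in the plan gives item 3d that role.
- *That a PK-biomarker correlation has been omitted, because Objective 5 names both.* It may sit in that separate SAP, so its absence here is not shown to be a gap.

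**Conclusion.** The point holds as a minor one. Items 3d and 3.3(3) plan an unadjusted correlation of on-treatment PK with a score that contains pre-entry variation. Baseline adjustment gives more power than the level at any positive ρ when exposure is independent of baseline. Both adjustment and change are much less prone than the level to a false association in the settings examined, but neither is clean in both.

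The direction does not depend on the exact inputs; the sizes do. They rest on an assumed ρ, exposure effect, PK-cognition correlation and PK sampling, and should be read as illustration. The primary comparison and the listed secondary comparisons are unaffected.

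**What to change.** Reword SAP section 4.2.3, item 3d, and section 3.3, item 3, along these lines:

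*DTG and MVC PK at weeks 24 and 48, each among participants assigned that drug, and the neurocognitive composite at the same week, by partial Spearman correlation adjusting for the pre-entry composite. The Spearman correlation of PK with change in the composite from pre-entry will be reported alongside with equal weight. Scatterplots of PK against the level are descriptive.*

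Add one sentence of interpretation: the two versions reduce but do not remove confounding by adherence, and adherence that changes with cognition during follow-up remains in both.

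The cost is SAP wording and a few lines of programming. The pre-entry composite is already needed for the primary outcome. The one downside is that a participant without a pre-entry score drops out of this analysis.
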